## INTRODUCTION

Antimicrobial use is a major contributor to the spread and emergence of antimicrobial resistance, a persistent public health problem. Antimicrobials are frequently prescribed in both hospitals and ambulatory care, but the majority of antimicrobial-prescribing is in outpatient settings. An estimated 30% of all outpatient antimicrobial use is unnecessary.

Audit-and-feedback is an effective strategy for improving antimicrobial-prescribing. Audit-and-feedback involves reviewing a clinician's antimicrobial-prescribing behavior and providing feedback to help the clinician adjust his/her performance. The use of audit-and-feedback for outpatient antimicrobial stewardship has been largely studied in primary care clinics with limited data in Emergency Departments and urgent care centers.

The Emergency Department (ED) is a major provider of medical care in the United States and, in turn, an important partner in efforts to improve antimicrobial-prescribing. The use of EDs has been increasing steadily over the past decade. In 2016, there were 145.6 million visits to EDs in the United States, or 46 visits per 100 persons. During these visits, ED clinicians prescribed 29 million antimicrobials. Prior studies have demonstrated several opportunities to improve antimicrobial-prescribing in EDs.

In this quasi-experimental pilot study, we evaluated whether the use of audit-and-feedback with peer-to-peer comparisons could reduce unnecessary antimicrobial use at 2 intervention EDs compared to 2 matched control EDs.

## METHODS

Study design: We performed a quasi-experimental pilot study with an interrupted time-series design and a matched-pair non-equivalent control group to evaluate the effect of a pilot intervention on clinicians at 2 participating EDs versus 2 control EDs. All EDs were affiliated with Veterans Affairs Medical Centers (VAMCs) in the midwestern United States.

Ethics approval: The clinical trial was registered on ClinicalTrials.gov, NCT03349567. The Institutional Review Boards (IRB) at the University of Iowa and Indiana University as well as the

Research & Development Committee of the Iowa City and Indianapolis VAMCs approved this study and waived written informed consent. All other sites were not engaged in research activities, so local IRB approval was not sought.

Site selection: First, we contacted VAMCs within two midwestern Veterans Integrated Service Networks (VISNs) to assess their interest in participating in this study. These 2 VISNs were chosen because they were among the few VISNs that had not implemented regional initiatives to improve antimicrobial use in ambulatory care.

Once two intervention sites were identified, we pulled a year of antimicrobial-prescribing data for all EDs within these same two midwestern VISNs. Eligible control sites had a baseline antimicrobial-prescribing rate (outpatient antimicrobial prescriptions dispensed per total ED patient-visits) that was similar to the intervention sites. Selection of controls on the pre-intervention outcome of interest minimized bias and reduced the impact of regression to the mean, which is a key threat when selecting poor performers in non-randomized trials. To further ensure that intervention and control sites were as similar as possible, control and intervention sites were also matched on their hospital complexity level, as defined by the VHA.

Intervention: The entire study period was 2-years in duration. The baseline period covered 1-year between 10/01/2017 through 09/30/2018, the implementation phase lasted one month (10/2018), and the intervention period spanned another 11 months, 11/01/2018 through 09/30/2019.

In 10/2018, the study team had meetings with all willing ED clinicians at the intervention sites. At intervention site 1, these meetings were face-to-face and took place during a two-day time frame when [name], an Infectious Disease (ID) physician, was present on-site. These one-on-one meetings with each clinician lasted 10-15 minutes and included a review of the clinician's individual antimicrobial-prescribing data (see feedback metrics), an anonymous comparison to his/her local peers, and a review of antimicrobial-prescribing guidelines. At intervention site 2, [name] enrolled ED clinicians by telephone while an on-site ID physician

([name]) met with clinicians in-person. The content of these meetings was identical to those at intervention site 1.

After the initial meeting, the study team e-mailed updated data to each participating clinician on his/her antimicrobial use. These e-mails were sent once every quarter. Overall, three e-mails were sent over the 12-month study period. E-mails were not sent after the fourth quarter, as the study had concluded by that point.

Beginning in late September 2018, a clinical pharmacist was assigned to the ED at intervention site 2 from 10a-10p every day. One of the clinical pharmacist's responsibilities was to ensure adequate antimicrobial selection. These pharmacists were not part of this trial, and the study team was only made aware of their presence as the intervention period was about to begin. To account for this, separate analyses were performed for intervention sites 1 and 2.

*Feedback metrics:* Feedback at the enrollment visit and in each quarterly e-mail update consisted of two metrics: 1) the clinician's total antimicrobial-prescribing volume adjusted for the total number of ED patient-visits, i.e. a total antimicrobial prescribing rate, and 2) the clinician's rate of prescribing antibiotics for uncomplicated viral acute respiratory infections (ARI), based on data from the VA's internal Academic Detailing website. The ARI metric included visits for acute bronchitis and non-specific upper respiratory tract infections but excluded visits for patients who were immunosuppressed, had chronic lung disease, or had a concurrent infection.

For the enrollment meeting with clinicians, both metrics were based on the year preceding the initiation of the study. Once the intervention period began, data on the clinician's total antimicrobial-prescribing rate was only drawn from the intervention period, which could include more than one quarter. Data on the ARI metric was only provided if the patient had seen  $\geq 8$  eligible ARI cases during the prior quarter; if there were not 8 eligible visits during the prior quarter, then more than one quarter of data could be included as long as the data was all from the intervention period.

At enrollment, clinicians were compared to their peers for both metrics. In subsequent e-mail communications, clinicians were compared to their peers and to their own prior performance for the ARI metric. For the total antimicrobial-prescribing rate, e-mails only compared clinicians to their personal baseline performance. The wording used in all feedback reports was based on the MITIGATE toolkit (Supplemental Table 1). All peer-to-peer comparisons were also demonstrated graphically in an attachment to the e-mail (Supplemental Figure 1).

To assess whether the clinician received the e-mail feedback, we requested a read receipt for all e-mail communication. The percentage of read receipts that were acknowledged was tracked over time.

We did not educate or provide feedback to ED clinicians at the two control sites. The control sites were not aware that their antimicrobial-prescribing was being monitored.

Outcomes: The primary outcome was the cumulative frequency of an outpatient antimicrobial prescription within 24 hours of the ED visit. ED visits that resulted in an inpatient admission within 24 hours after the visit were not eligible for inclusion in the outcome. Antimicrobials were defined as all agents included in the National Healthcare Safety Network's (NHSN) Antimicrobial Use and Resistance Module. On a monthly basis, the cumulative number of outpatient antimicrobials prescribed by the ED and the total number of eligible ED visits were used as the numerator and denominator, respectively. This outcome was chosen as it would not be influenced by diagnostic shifting.

The secondary outcome was the proportion of ED visits associated with an outpatient antibiotic prescription within 24 hours of the ED visit; it was calculated similar to antimicrobial use. Antibiotics were defined as all antibacterial agents, as defined by the NHSN's Antimicrobial Use and Resistance Module.

The ARI metric, as defined above, was captured across all clinicians at the control and intervention sites. Guideline-concordant management was assessed using manual chart

reviews (see below). Other secondary outcomes were measured from 24 hours after the ED visit up to 30 days after the visit. These secondary outcomes included testing for the presence of *Clostridioides difficile*, confirmed *C. difficile* infection (CDI), return ED visit, late antimicrobial use, late antibiotic use, and admission to a VHA acute-care facility. CDI linked to a visit was confirmed if the patient had a positive *C. difficile* test and a qualifying antibiotic (metronidazole, oral vancomycin, or fidaxomicin) was dispensed to the patient within 7 days of the positive *C. difficile* test. Visits that occurred from 24 hours up to 30 days after the prior visit were recorded as a return ED visit. ED visits that occurred after 30 days from the prior ED visit were considered as independent visits. Primary and secondary outcomes, except return ED visits, included all eligible visits in the denominator.

Data on oral antimicrobial prescriptions, demographics, comorbidities, infections, and laboratory data for *Clostridioides difficile* for ED visits during the study period were extracted from the Corporate Data Warehouse (CDW) using the VA Informatics and Computing Infrastructure (VINCI). The *International Classification of Diseases*, Tenth Revision (ICD-10) codes were used to identify existing comorbidities and infection diagnoses linked to the ED visit.

**Statistical Analysis:** An interrupted times series analysis was used to evaluate the effect of audit-and-feedback between the intervention and control sites. The crude differences in patient characteristics from baseline to intervention periods were assessed for intervention and control sites using Fisher's exact test and Wilcoxon rank-sum test. Monthly proportions of antimicrobial and antibiotic use were calculated at each site for the baseline and intervention time periods. Segmented regression analysis was conducted using generalized linear models to estimate change in monthly antimicrobial and antibiotic prescription rates between baseline and intervention periods for intervention and control sites, respectively. Models were adjusted for continuous variables for time (months before, during, and after implementation). The estimate for time during implementation was used to calculate the immediate change in prescription rates and was reported as incident rate ratios (IRR) with 95% confidence intervals (CI). Indicator

variables for the four seasons were also included in each model to adjust for seasonal trends. An R-side random statement was included in each model to vary the degree of overdispersion for each facility. Finally, a difference-in-difference estimate was reported for the change in monthly prescription rates between intervention and control sites in the intervention period while controlling for changes in the baseline period. A Poisson regression model with log link was used to estimate the rate of secondary outcomes. Models were adjusted for time as a continuous covariate, an indicator for month of implementation of intervention (October 2018), and included random effects to account for repeated measures among sites each month during the study period. An interaction variable for the study period (baseline or intervention) and site (intervention or control) was included in the model to estimate the IRR and 95% CIs.

*Manual chart reviews to assess guideline-concordant management:* Patient-visits were eligible for manual chart review if the visit met the following criteria: 1) a patient's first ED visit during the study period; 2) a qualifying infection diagnosis, as defined by ICD-10 codes, and 3) no evidence of immunosuppression. Qualifying diagnoses were acute bronchitis, acute exacerbations of chronic obstructive pulmonary disease (AE-COPD), acute sinusitis, cystitis, pharyngitis, and upper respiratory tract infection (URI) (Supplemental Table 2).

Immunosuppression was defined as having a diagnosis of lymphoma, leukemia, HIV/AIDs, or organ transplantation during the 12 months prior to presentation or receipt of an immunosuppressive medication, which was defined as follows: prednisone or steroid equivalent at a dose  $\geq 20$  mg/day during the 30 days prior to admission, chemotherapy within the 30 days prior to admission, or an anti-rejection medication, biologic agent or a disease-modifying anti-rheumatic drug within the 3 month prior to admission. At each of the 4 EDs, eligible patient-visits were randomly chosen for review. Two independent, blinded reviewers evaluated selected medical records while using defined algorithms (Supplemental Figures 2-7). Reviewers assessed the accuracy of the diagnosis and, if necessary, re-classified the infection type; they also evaluated a decision to prescribe or not prescribe antibiotics as well as the appropriateness

of antibiotic selection and duration. Reviewers consisted of a fourth-year medical student, an Internal Medicine resident physician, and an Infectious Disease fellow physician. If the initial reviewers' assessment were discordant, a third reviewer, who was not blinded, reviewed the medical record. The third reviewer ([name]) had to evaluate 128 (26.7%) charts during the baseline period and 135 (29.7%) during the intervention period. The goal was to include at least 110 adjudicated charts per site for the baseline and intervention periods.

Guideline-concordant management was defined as either prescribing an antibiotic when indicated or not prescribing an antibiotic when not indicated. Guideline-concordant antibiotic selection was defined as prescribing an antibiotic recommended by professional guidelines, as defined by our protocols (Supplemental Figures 2-7). Guideline-concordant duration was defined as prescribing an antibiotic for a duration that was  $\leq 2$  days shorter and  $\leq 2$  days longer than what is recommended by professional guidelines.

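### Analysing the two intervention sites separately does not account for the pharmacist at site 2: that estimate is feedback plus pharmacist, and the plan does not say so

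*Combined protocol and SAP*

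**What the plan says.** The Introduction sets the question: "we evaluated whether the use of audit-and-feedback with peer-to-peer comparisons could reduce unnecessary antimicrobial use at 2 intervention EDs", compared with two matched controls. Methods (Study design) describes an interrupted time series with "a matched-pair non-equivalent control group".

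Methods (Intervention) gives the dates: "The baseline period covered 1-year between 10/01/2017 through 09/30/2018". October 2018 is the implementation month, when the feedback meetings were held, and the intervention period runs from November 2018 through September 2019.

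The same section discloses an unplanned change at one site: "Beginning in late September 2018, a clinical pharmacist was assigned to the ED at intervention site 2 from 10a-10p every day". On duties it says: "One of the clinical pharmacist's responsibilities was to ensure adequate antimicrobial selection". The pharmacists were outside the trial, and the team learned of them just before the intervention period. The stated response is: "To account for this, separate analyses were performed for intervention sites 1 and 2".

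Methods (Statistical Analysis) presents the time-series analysis as estimating the effect of audit-and-feedback. The models contain time terms, season indicators and facility-specific overdispersion. There is no pharmacist term and no use of the pharmacist's hours. The main contrast is worded for intervention against control sites as groups: "a difference-in-difference estimate was reported for the change in monthly prescription rates between intervention and control sites in the intervention period". The secondary-outcome interaction is also coded intervention or control. Nowhere is the site 2 estimate described as a combined effect.

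**The concern.** Splitting the analysis by site keeps the pharmacist out of the site 1 estimate. It does nothing to separate pharmacist from feedback within site 2, where both arrived at nearly the same time. A control site removes only changes that it shares, and no control is described as gaining a pharmacist.

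A reader told that the pharmacist was accounted for could take the site 2 result as evidence on feedback alone. Similar results at the two sites could be read as replication, and different results as variation in how well feedback works. Neither reading is supported. One of only two intervention departments is affected.

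**Working it through.** The plan states no figure for this point, so there is none to reproduce. The check is whether the two effects can be told apart in site 2 monthly data.

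**Inputs from Methods (Intervention).** Baseline October 2017 to September 2018 (12 months); October 2018 is implementation; November 2018 to September 2019 is intervention (11 months). The pharmacist started in late September 2018.

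**Assumptions.** The exact start date is not given, so the pharmacist is taken to cover d = 1, 5 or 10 of the 30 days of September. October 2018 is set aside, which equals giving it its own indicator, as the secondary-outcome models do. That leaves 12 + 11 = 23 months.

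**Coding.** Feedback F = 0 in the 12 baseline months and 1 in the 11 intervention months. Pharmacist P = 0 through August 2018, d/30 in September 2018, and 1 from November 2018. F and P differ in one month only, by d/30.

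**Step 1: overlap.** r is the correlation of F and P over the 23 months. With no other covariates, adding P multiplies the standard error of the F step by 1/√(1 − r²). The last column uses an assumed segmented model (intercept, trend, step, change in trend, three season indicators, equal month weights), with and without P.

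| September days d | r | SE ratio, no covariates | SE ratio, segmented model |
|---|---|---|---|
| 10 | 0.991 | 7.4 | 3.6 |
| 5 | 0.998 | 14.8 | 7.8 |
| 1 | 0.9999 | 74.9 | 42 |

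The segmented design with P has 8 columns and rank 8, so separation is possible in principle but very imprecise. If the pharmacist is coded from October (d = 0), r = 1 and the rank falls to 7 of 8: no separation at all.

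**Step 2: other codings of October.** If October is kept and counted as feedback, the variance of the feedback step rises 15.3-, 73.1- and 2130-fold for d = 10, 5 and 1. The SE ratios are √15.3 = 3.9, √73.1 = 8.5 and √2130 = 46. If October is instead counted as pharmacist but not yet feedback, the ratio is only about 1.3. Separation then rests on that single month, when the feedback meetings were themselves taking place, so this coding is not credible.

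**Step 3: effect on the site 2 estimate.** On the rate-ratio scale, with the pharmacist's ratio taken to be the same with or without feedback,

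site 2 IRR = feedback IRR × pharmacist IRR, so feedback IRR = site 2 IRR ÷ pharmacist IRR.

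The documents give neither value. For an assumed site 2 IRR of 0.90:

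| Assumed pharmacist IRR | Implied feedback IRR |
|---|---|
| 0.90 | 0.90/0.90 = 1.00 |
| 0.95 | 0.90/0.95 = 0.947 |
| 1.00 | 0.90/1.00 = 0.90 |
| 1.05 | 0.90/1.05 = 0.857 |
| 1.10 | 0.90/1.10 = 0.818 |

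A pooled estimate carries part of the same effect. With no feedback effect and equal weights on the log scale, a pharmacist IRR of 0.90 gives √0.90 = 0.949 over the two sites.

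**The case against.** The strongest reply is that the plan has largely dealt with this. One paragraph gives the pharmacist's start, hours, duty and independence from the trial, and then reports separate site analyses. The claim to have accounted for the pharmacist can be read as meaning only that site 1 was kept clean; no text says site 2 was adjusted. The documents contain no results or discussion, so no feedback-alone conclusion is actually drawn from site 2.

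Relevance to the primary outcome is also unproven. It is defined as follows: "The primary outcome was the cumulative frequency of an outpatient antimicrobial prescription within 24 hours of the ED visit". The only documented pharmacist duty concerns selection, for 12 of 24 hours. Finally, the rate ratios above are illustrations, and the standard-error ratios describe a model that the plan does not propose.

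Much of this stands. The disclosure and the split deserve credit, the pharmacist effect may be small for any-antimicrobial use, and its direction is unknown. The standard-error ratios show how little the data can separate the two effects; they do not measure an error in the planned estimate.

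It does not remove the point. The sentence is unqualified, and the statistical section still calls the estimate the effect of audit-and-feedback. Selection is described as one duty among several, so an effect on whether to prescribe cannot be excluded. Appropriateness of antibiotic selection is itself assessed in the chart reviews, where the overlap is most direct.

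**Conclusion.** The concern holds and should be fixed. The separate analyses account for the pharmacist at site 1 only. At site 2 the stated monthly analysis estimates feedback and pharmacist together, and the plan does not label it so.

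The near-coincidence follows from the plan's own dates. The exact correlations depend on the assumed 1 to 10 September days, and the standard-error ratios also on the assumed model form. How far the site 2 estimate departs from the feedback effect cannot be determined from the documents.

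A lesser gap is that the group wording of the contrasts in the statistical section is compatible with per-site models but does not state them, and the text does not say which control is matched to which intervention site.

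**What to change.** 1. **Relabel.** In Methods (Intervention), replace the claim that the pharmacist was accounted for with a statement that site 2 estimates feedback plus ED pharmacist, and that only site 1 against its matched control is free of the pharmacist. Show both site estimates side by side. Draw no feedback-alone conclusion from any estimate that includes all site 2 visits, pooled ones included. If a lead site is chosen after data collection, label that choice post hoc.
2. **Write out the contrasts.** In Methods (Statistical Analysis), name the matched pairs and state that the primary, secondary and chart-review contrasts are each run per intervention site against its own control.
3. **Optional and exploratory.** If visit times are available, compare site 2 visits inside and outside 10a-10p with the matched control in the same hours. The 24-hour outcome window suggests that times exist, but they are not among the listed extracted data. Carry-over between shifts and case-mix differences limit the comparison. If a share p = 0.6 to 0.8 of visits falls inside those hours (assumed), the outside-hours standard error is 1/√(1 − p) = 1.58 to 2.24 times that of all visits, and that of the inside-outside difference 1/√(p(1 − p)) = 2.04 to 2.50 times.

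**Cost.** Items 1 and 2 need wording and analysis only; charts were already sampled at each department. Feedback-alone inference then rests on one intervention and one control department, without replication, so any other local change at either is also confounded with feedback. The standard error is √2 = 1.41 times that of an equal-weight two-site contrast. For chart review at the target of 110 per site and period, with proportion 0.5 and binomial variation only, the 95% half-width of a one-pair difference-in-difference is 1.96 × √(4 × 0.25/110) = 18.7 percentage points, against 1.96 × √(4 × 0.25/220) = 13.2 for both pairs. Relabelling exposes this limit; it does not create it.

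### VHA admissions and return ED visits in the first 24 hours after ED discharge are not counted, so a null result for these two outcomes says nothing about early deterioration

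*Combined protocol and SAP*

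**What the plan says.** All of the relevant text is in METHODS of the combined protocol and SAP.

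- **Primary outcome (Outcomes).** "The primary outcome was the cumulative frequency of an outpatient antimicrobial prescription within 24 hours of the ED visit". The window is 0 to 24 hours.
- **Eligibility (Outcomes).** "ED visits that resulted in an inpatient admission within 24 hours after the visit were not eligible for inclusion in the outcome". Admission straight from the ED is not separated from discharge followed by admission.
- **Harm window (Outcomes, secondary).** "Other secondary outcomes were measured from 24 hours after the ED visit up to 30 days after the visit". The list comprises *C. difficile* testing, confirmed *C. difficile* infection, and "return ED visit, late antimicrobial use, late antibiotic use, and admission to a VHA acute-care facility".
- **Return visits (same paragraph).** "Visits that occurred from 24 hours up to 30 days after the prior visit were recorded as a return ED visit". Visits more than 30 days after the prior one are independent visits. No class is given for a visit before 24 hours.
- **Denominator (same paragraph).** "Primary and secondary outcomes, except return ED visits, included all eligible visits in the denominator". The eligibility rule therefore carries into the admission analysis.
- **Analysis (Statistical Analysis).** "A Poisson regression model with log link was used to estimate the rate of secondary outcomes", with a period-by-site interaction giving the IRR. No count or sensitivity analysis of admissions or ED returns before 24 hours is described.

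**The concern.** The intervention aims to lower prescribing. One of its two feedback metrics is each clinician's total antimicrobial rate, so the pressure to prescribe less is not confined to viral respiratory infection. Admissions and ED returns are the natural check that patients who went without treatment did not get worse. If both start at 24 hours, the trial could report no increase in either without having looked at the first day.

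The eligibility rule adds a second problem. Whether a discharged patient is admitted within 24 hours is known only after the prescribing decision, and that decision could influence it. Matched controls remove shared trends, but they would not remove an early rise caused by the intervention itself.

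**Working it through.** The documents state no event rate, timing distribution or visit count that bears on this point, so there is no figure to reproduce. The check is one of logic, followed by illustrations in which every input is assumed.

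**1. Where each early event goes**

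| Event before 24 hours | Index visit | Event counted as harm? |
|---|---|---|
| Discharged, then admitted; exclusion covers any admission within 24 hours (plain reading) | Dropped | No, before the window |
| Discharged, then admitted; exclusion covers only direct admission (narrow reading) | Kept | No, before the window |
| Returns to the ED, not admitted | Kept | No; neither a return nor an independent visit |
| Outpatient antimicrobial given at such a return | Kept | No; it can count in the primary outcome, as prescribing |

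On either reading of the exclusion, no admission or ED return in the first 24 hours is counted as harm.

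**2. Share of 30-day events in the first day (assumed curves)**

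The share is f = F(1)/F(30), where F is the cumulative distribution of days to the event. The means below are those of the curve before truncation at 30 days.

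- Exponential, highest rate at hour zero: f = (1 − e^(−1/μ))/(1 − e^(−30/μ)). For μ = 5 days, 0.1813/0.9975 = 18%. For μ = 7, 10 and 14 days, f = 13%, 10% and 8%.
- Delayed onset (gamma, shape 2, same means): 6.2%, 3.4%, 1.8% and 1.0%.
- Even spread over 30 days: 1/30 = 3.3%.

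The range is about 1% to 18%, and the choice of curve decides where in it the share falls.

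**3. What the planned IRR would miss**

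IRR(0-30 days) = f × R_early + (1 − f) × R_late, where R_early and R_late are the rate ratios before and after 24 hours. Set R_late = 1.00. The planned IRR is then 1.00 whatever R_early is, and the 0-30 day IRR is 1 + f × (R_early − 1):

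| f | R_early = 1.5 | R_early = 2.0 |
|---|---|---|
| 1% | 1.005 | 1.01 |
| 10% | 1.05 | 1.10 |
| 18% | 1.09 | 1.18 |

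**4. Effect of the exclusion on the primary IRR**

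Let p be the prescriptions per discharged visit, the same in both periods. Let e be the share of discharged visits admitted within 24 hours, none of them with a prescription. The planned rate is p/(1 − e), so the IRR is multiplied by (1 − e₀)/(1 − e₁), where e₀ and e₁ are the baseline and intervention values. With e₀ = 1% and e₁ = 2%, this is 0.99/0.98 = 1.010, whatever the value of p. The shift is about 1%, upward, so it would slightly understate a reduction in prescribing.

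**The case against.** The best defence is that the exclusion has a plain rationale. A patient admitted within 24 hours has little opportunity to receive an outpatient prescription, the exclusion window matches the primary outcome window, and a fixed 24-hour rule copes with boarded patients and late coding. This stands as a reason for excluding patients admitted from the ED. It does not explain why patients who were discharged and then admitted are counted nowhere.

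A reader might infer more than the documents support:

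- *That all early bounce-backs are removed from the trial.* Only those ending in admission can lose the index visit. For a return without admission, only the event goes uncounted.
- *That every safety outcome is affected.* Late antimicrobial and antibiotic use must start at 24 hours because the primary outcome occupies the first day. Nothing in the documents shows that the start matters for the *C. difficile* outcomes. The point concerns two of six outcomes.
- *That the comparison is biased.* The rule is the same at all sites and in both periods. It biases the comparison only if the intervention changes early rates, and nothing in the documents shows that it does. The respiratory feedback metric is limited to uncomplicated viral infection, although the total-rate metric is not.
- *That failures of untreated infection cluster in the first day.* The documents contain no timing data.

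Two further replies have partial force. If under-treatment also raised later events, the planned outcomes would register it. And the chart review looks at under-treatment: "Guideline-concordant management was defined as either prescribing an antibiotic when indicated or not prescribing an antibiotic when not indicated". But that is a process measure on a sample from six diagnoses, and its definition does not cover deterioration.

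**Conclusion.** The gap is real and follows from the text alone: for VHA admission and return ED visit, the first 24 hours after ED discharge are uncovered. On the plain reading, eligibility is also conditioned on an event after the prescribing decision. The planned IRRs for these two outcomes should be read as applying from 24 hours onward only.

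The size cannot be derived from the documents. The first-day share and the IRR illustrations rest on assumed timing curves and assumed rate ratios, with no change after 24 hours. The 1% shift in the primary IRR rests on an assumed doubling of early admissions, none of them with a prescription. The primary conclusion of this pilot is therefore unlikely to turn on the point; the safety statement is what gains. This is a cheap improvement, not a flaw that undermines the trial.

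**What to change.** 1. Keep excluding visits whose own ED disposition was admission or transfer. Retain every visit discharged from the ED, whatever happens next.
2. For VHA admission and return ED visit only, count events from ED discharge to 30 days, at least as a sensitivity analysis beside the planned window.
3. Report the 0-24 hour admissions and ED returns by site and period, and state how a return before 24 hours is classified.
4. Leave the 24-hour start for late antimicrobial use, late antibiotic use and the *C. difficile* outcomes.

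The cost is revised outcome wording and a filter on disposition or discharge time. Applying the 24-hour exclusion already requires finding the early admissions, so those events can be identified; that disposition or discharge time is available in the warehouse data is an assumption. The downside is that a rule is needed to assign the admission where disposition is missing or a boarded patient is coded late.
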